Data management - Data will be stored in a secured, centrally located REDCap database. Investigators will oversee the REDCap database setup, data management, audit and edit plans to ensure data accuracy and completeness, and creation of the study's codebook with precise definitions and coding of all variables. A double-checking mechanism will be set up to ensure data completeness and accuracy. Strategies are set up for handling missing data, which are described below.

VI. Data Analysis, Sample Size and Statistics - [name], a biostatistician with the University of Minnesota School of Public Health, will analyze data from the RCT. Similar to standard methods for factorial designs in other therapeutic areas, analyses to address the primary aims will be a test of the main effect of the randomized interventions (i.e., report type and counseling type). All analyses will be by intention-to-treat, and include all participants randomized, regardless of whether they are lost to follow-up. The primary outcome measures will be a dichotomous comparison of 24-hour quit attempts (yes/no) at the time of the three-week follow-up, three-month follow-up, and six-month follow up and subject-reported readiness to quit based on the contemplation ladder among those who have not quit smoking. Secondary outcomes include cotinine-verified abstinence at three and six-months and use of smoking cessation services (dichotomous outcome) at 3 weeks, 3 and 6 months. Initially assessment will focus on the main effect of Report condition (Report vs. Usual Care) averaging or "pooling over" the Counseling condition on the continuous (readiness to quit) and dichotomous outcomes (24-hour quit attempt, abstinence, use of smoking cessation services) using a two sample t-test of the difference in the mean response and two-sided Wald-type test [60] of the difference in proportions, respectively, with a 0.05 significance level. Exact tests (e.g., Barnard's exact test) may be used if the number of successes (e.g., quit attempts, abstinence) is

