small. Separate analyses will be performed at each measurement time point (e.g., three-weeks, three-months, and six-months). A similar set of analysis can be performed to assess the main effect of the counseling condition. Logistic and linear models (for the dichotomous and continuous outcomes) with covariates for report condition, counseling condition, and their interaction will be used to assess if the Report and Counseling conditions significantly interact. If the interaction is significant, there will be an examination of whether there is a significant difference between the Report and Usual Care within each level of the Counseling condition. As an exploratory analysis to help guide future studies, a logistic regression model with quit attempt (yes/no) as the response will be utilized. Possible covariates include intervention group, gender, age, number of pack years, interest in quitting at baseline, risk perception at baseline, number of previous quit attempts, and findings from the CT scan, and their interaction with the Report condition. Similar models could be constructed for the other outcomes (abstinence, use of use of smoking cessation services). Additional linear regression models will be constructed for the other outcomes (readiness to quit). Additionally examination will be on whether or not changes in readiness to quit at 3 weeks mediate quit attempts, use of smoking cessation resources, and abstinence at 3 and 6 months using structural equation modeling.

Sample Size: The proposed RCT is powered for a main effects analysis of the Report (averaged over the Counseling condition) for the following outcomes a) at least one 24-hour quit attempt within 6 months of the CT scan b) accessing either formal cessation programs and/or FDA-approved medications within 6 months and c) readiness to quit as measures by the contemplation ladder.

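### Optional gain: pre-specify adjustment for Counseling and a pre-randomisation readiness value in the Report main-effect tests

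*Combined protocol and SAP*

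**What the plan says.** Section VI (Data Analysis, Sample Size and Statistics) first assesses the Report main effect by "averaging or 'pooling over' the Counseling condition", "using a two sample t-test of the difference in the mean response and two-sided Wald-type test" for the readiness and binary outcomes respectively. Readiness is compared only "among those who have not quit smoking".

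Counseling enters a model only to test its interaction with the Report. Baseline variables come later: "As an exploratory analysis to help guide future studies, a logistic regression model with quit attempt (yes/no) as the response will be utilized", with possible covariates that include "interest in quitting at baseline, risk perception at baseline, number of previous quit attempts". Linear models for readiness are also foreseen, but no covariates are named for them and they are not the main analysis. The Sample Size text claims adequate power for the planned differences and reasonable power in many scenarios for smaller ones.

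Section V schedules the readiness assessment at 3 weeks, 3 months and 6 months and describes no baseline measurement. Section VI nevertheless lists baseline interest in quitting and asks whether "changes in readiness to quit at 3 weeks mediate quit attempts". A change at 3 weeks needs an earlier value.

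**The concern.** In a 2 by 2 factorial trial with a plausible baseline predictor, an unadjusted pooled comparison leaves explainable variance in the error term. That includes variance due to Counseling, which the trial itself creates. The result is not biased, but it is less precise than it need be. This matters most for effects below the planned ones, where the plan also claims useful power.

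Two further points affect how adjustment could be used. The timing of the baseline value is not stated, and only a value recorded before randomisation is a safe covariate. Also, the readiness comparison is confined to a group formed after randomisation, so it is not a purely randomised contrast whether adjusted or not.

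**Working it through.** **Inputs.** Table 2 and its note give 400 participants, two-sided 0.05 for the main effect, a ladder SD of 2.9, readiness differences of 1.5 and 1.0, and four cell percentages per binary row. Equal allocation is assumed (200 v 200, 100 per cell); it reproduces the table. The baseline–outcome correlation r is not given and is assumed throughout.

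**Reproducing Table 2.** For readiness, SE = 2.9 × √(2/200) = 0.290. Noncentral-t power is 93.1% for 1.0 point (printed 93.2%) and 99.93% for 1.5 points (printed 99.9%). For binary outcomes, the pooled variance is [p0(1−p0) + p1(1−p1)]/200 and power is Φ(difference/SE − 1.96). This gives 98.7, 89.0, 91.6 and 80.7%, against printed 98.7, 89.2, 92.4 and 81.2%.

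**Counseling alone, binary.** The stratified variance is the sum of p(1−p) over the four cells, divided by 400. Example, smaller services effect: pooled (0.09 + 0.16)/200 = 0.001250; stratified (0.0475 + 0.1275 + 0.1275 + 0.1875)/400 = 0.001225, a 2.0% reduction. Over the four rows the variance falls by 2.0–4.3% and power rises by 0.3–0.8 points.

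**Counseling plus baseline, binary.** Adjusted variance = stratified variance × (1 − r²).

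| Outcome and difference | Planned test | Counseling only | r = 0.2 | r = 0.3 | r = 0.4 |
|---|---|---|---|---|---|
| Quit attempt, 20 points (planned) | 98.7% | 98.9% | 99.2% | 99.4% | 99.6% |
| Quit attempt, 15 points | 89.0% | 89.7% | 90.9% | 92.2% | 94.1% |
| Services, 12.5 points (planned) | 91.6% | 92.3% | 93.2% | 94.4% | 95.8% |
| Services, 10 points | 80.7% | 81.5% | 83.0% | 85.0% | 87.6% |

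For the two smaller effects, the gain equals an unadjusted trial of about 425 to 489 participants instead of 400.

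**Readiness.** Residual SD = 2.9 × √(1 − r²): 2.77 at r = 0.3 and 2.51 at r = 0.5.

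| Case | Unadjusted | r = 0.3 | r = 0.5 |
|---|---|---|---|
| Power, 1.0 point, 200 v 200 | 93.1% | 95.0% | 97.8% |
| Power, 1.0 point, 190 v 170 | 90.3% | 92.7% | 96.4% |
| Difference detectable with 80% power, 200 v 200 | 0.81 | 0.78 | 0.71 |
| Equivalent unadjusted N, 400/(1 − r²) | 400 | 440 | 533 |

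The 190 v 170 row removes 5% and 15% of 200. These are the plan's expected 3-week quit-attempt rates, used as a proxy for exclusion, and the row shows the sample-size effect only. At 1.5 points the gain with 200 v 200 is under 0.1 point. If 2.9 is the SD within each cell, Counseling adjustment alone moves 1.0-point power from 92.4% to 93.1%.

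**Simulation check, binary** (4,000 trials per scenario, 100 per cell, raw Wald test v standardised risk difference; run once). At a log-odds of 0.8 per SD of baseline, power for the smaller effects went from 89.1% to 93.2% (quit attempts, r about 0.33) and from 82.0% to 84.9% (services, r about 0.25). Even 1.2 per SD gave r of only 0.34–0.36 for services, so r = 0.4 is optimistic there. With an uninformative baseline nothing was lost: 89.7% raw v 90.1% adjusted, and 82.6% v 83.1%. Null rejection was 5.1–5.6% raw and 5.3–5.6% adjusted.

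**What adjustment does not cure.** In 6,000 trials per scenario there was no Report effect on readiness, and 5% v 15% were removed as quitters. The assumed correlation between readiness and quitting was 0.3–0.7. The unadjusted test rejected in 7.3–21.9% of trials and the adjusted test in 6.9–20.5%. With 10% v 20% removed, the ranges were 7.3–20.3% and 6.9–19.0%. With equal 5% exclusion both stayed near 5%.

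**The case against.** The strongest reply is that nothing is broken. The tests are standard for a factorial design, they are not biased by omitting covariates, and Table 2 reproduces. At the differences the plan calls meaningful or of interest, printed power is already 98.7%, 92.4% and 99.9%. Regression with baseline covariates is already foreseen; only its rank would change. All of this stands and is why the point is optional.

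The gain rests mostly on an assumed r. The part that needs no assumed r, Counseling adjustment, adds at most 0.8 points, about the gap between this formula and the printed planned-services figure (91.6% v 92.4%). For planned services the simulation also showed a smaller gain (93.0% to 93.6% at r about 0.17) than the formula gives at r = 0.2 (91.6% to 93.2%). That is a fair reason to call the gain modest.

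The largest readiness gains attach to a comparison distorted by removing quitters. This stands too: more precision there is useful only once the restriction is addressed. The exclusion rates used are quit attempts, not quits.

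No gain was computed for Quitline calls (the primary endpoint in Section III), cotinine-verified abstinence or the 3-week quit-attempt test. Sparse outcomes and missing baseline values also need a rule. These points limit the scope of the proposal but do not defeat it.

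No benefit is claimed for the comparisons within Counseling levels, which the plan makes only when the interaction is significant.

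**Conclusion.** The point holds as a low-priority improvement, not a defect. Nearly all the benefit comes from the baseline value. It amounts to about 2 to 5 points of power for a 1.0-point readiness difference (r = 0.3–0.5) and about 2 to 7 points for the smaller binary effects (r = 0.2–0.4). It is under 0.1 point for readiness and at most about 1 point for quit attempts at the planned effects, and 1.6 to 4.3 points for planned services. These figures assume equal allocation, 400 analysed unless stated, and values of r that the documents do not supply. Confidence is medium for that reason. Stating when baseline readiness or interest in quitting is recorded is worth doing whatever the power gain, because the exploratory and mediation analyses depend on it.

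**What to change.** - **Readiness:** pre-specify a linear model with Report, Counseling and baseline readiness, or baseline interest in quitting if that is what is collected.
- **Binary outcomes:** pre-specify a risk difference standardised from a logistic model with the same covariates. If no baseline value exists, use a Counseling-stratified risk difference. Either keeps the difference-in-proportions scale; an adjusted odds ratio would be a different estimand.
- **Sensitivity analyses:** keep the unadjusted t-test and Wald test. Retain the plan's exact-test option for sparse outcomes; Table 2 implies about 5 events in the usual-care services cell (5% of 100).
- **Baseline value:** state that it is recorded before randomisation and how missing values are handled. If it is not already collected, add the contemplation ladder to the consent call. Section IV describes that call for HealthPartners; confirm the equivalent step at Michigan.
- **Limit:** state that adjustment does not address the restriction of readiness to non-quitters, and handle that separately.

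If the baseline value is already collected, the cost is SAP wording and standard regression. If not, it is one extra question before randomisation, with the procedural and ethics-board changes that this needs at both recruiting systems.

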Power for these primary hypotheses are shown in Table 2 assuming 400 total subjects under different assumptions concerning the average response within each of the randomized groups. A difference of 20% and 12.5% is considered between the Report and Usual Care conditions to be of interest for the percentage of subjects with at least one 24-hour quit attempt and accessing cessation programs/medication within 6 months. Similarly, an average difference of 1.5 on the contemplation ladder is considered meaningful. Table 2 indicates there is sufficient power to detect these differences and even reasonable power across many scenarios to detect smaller effects for the main effect of the Report. Additionally, Table 2 demonstrates that there is adequate power to detect a significant effect of the Report within each level of the counseling condition at the 0.1 significance level.

Concerning 6-month abstinence, differences were considered between the Report and Usual Care between 5-10% to be meaningful. As a Phase II study, it is not powered to detect a significant main effect for the Report for the 6-month abstinence outcome. However, Table 3 demonstrates that across a range of plausible scenarios there is sufficient power for a composite test of whether or not the probability of abstinence at 6 months is the same across all 4 arms and whether or not the Report + Counseling is different than Usual Care.

As part of the analysis, it is expected that Report Only compared to Usual Care will significantly increase readiness to quit, quit attempts, and accessing of programs/medications. It is also expected that the Report + Counseling will produce significantly higher 7-day point prevalence abstinence at 6 months than Usual Care with the other two conditions intermediate. In particular, it is expected that the combination of counseling and the Report will be more effective in increasing readiness to quit, quit attempts, use of formal programs and/or medications and abstinence than the other three conditions. Additionally, it is expected that 5% in the

Outcome	Percentage or Mean				Power to Detect a Significant Effect of Report		
	Usual Care	Report Only	Usual Care + Counseling Only	Report + Counseling	Main Effect (averaged over counseling conditions)	Within No Counseling Condition	Within Counseling Condition
24 hour quit attempts	20%	40%	40%	60%	98.7%	93.5%	89.3%
	20%	35%	35%	50%	89.2%	77.7%	69.4%
Accessing Services and/or Medication	5%	17.5%	17.5%	30%	92.4%	88.9%	67.6%

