	5%	15%	15%	25%	81.2%	77.2%	55.1%
Readiness to Quit	6.0	7.5	7.5	9.0	99.9%	97.8%	97.8%
	6.0	7.0	7.0	8.0	93.2%	78.6%	78.6%

the Imbio report and usual CT scan report. Power calculations assume total N=400 and the use of a two-sided test with a 0.05 significance level for the main effect and 0.10 significance level for the effects within each counseling condition level. The power calculation for readiness to quit assume a standard deviation of 2.9 on the contemplation ladder.

Usual Care condition will make a quit attempt (24-hour quit) versus 15% in the Report condition at the time of the 3-week follow-up. The Report will yield significantly greater percentage of subjects reporting a quit attempt at 3 and 6 months.

VII. Title 21 FDA Device Trial Regulations

The IMBIO **Patient Smoking Cessation Report** is currently preparing to undergo the proposed RCT in preparation for eventual FDA approval as a medical device. This trial will be run under the non-significant risk (NSR) section of Title 21 FCR 812.2(b) and will follow the abbreviated trial requirements contained therein. CFR 812.2(b) is uploaded with this application. Also uploaded is Title 21 CFR 56.111, which gives the IRB criteria for approval of NSR clinical device research under the abbreviated requirements associated with FCR 812.2(b).

The IMBIO Patient Smoking Cessation Report, as an NSR device, is not required to seek IDE approval through the FDA prior to starting the clinical trial proposed in this application. IRB agreement that this device qualifies as an NSR device will suffice in lieu of a formal IDE application, as long as said determination of NSR status is transcribed into formal IRB minutes.

This clinical trial will be monitored by the sponsor of the trial, IMBIO, LLC, in accordance with the monitoring requirements found in Title 21 CFR 812.46.

Following the conclusion of the clinical trial proposed in this application, the sponsor will approach the FDA for approval or clearance as a medical device.

VIII. Study Timeline

Phase II Work Plan	2016			2017												2018												2019															
	Oct	Nov	Dec	Jan	Feb	Mar	Apr	May	June	July	Aug	Sept	Oct.	Nov.	Dec.	Jan	Feb	Mar	Apr	May	June	July	Aug	Sept	Oct.	Nov.	Dec.	Jan	Feb	Mar	Apr	May	June	July	Aug.								
Recruit RCT participants																																											
SUBMIT mayo IRB application (with questionnaire developed in SA2)																																											

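### The mediation model counts quit attempts and resource use from before 3-week readiness is measured, so for those events the order of mediator and outcome cannot be established

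*Combined protocol and SAP*

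**What the plan says.** Among the supplementary analyses in Section VI, the plan asks whether "changes in readiness to quit at 3 weeks mediate quit attempts, use of smoking cessation resources, and abstinence at 3 and 6 months". The mediator is the change in readiness recorded at the 3-week call.

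The windows for two of these outcomes appear only in the Sample Size paragraph of the same section. Attempts are counted as "at least one 24-hour quit attempt within 6 months of the CT scan" and resource use as "accessing either formal cessation programs and/or FDA-approved medications within 6 months". Both windows include the first three weeks. The analysis paragraph lists the primary attempt outcome as "24-hour quit attempts (yes/no) at the time of the three-week follow-up, three-month follow-up, and six-month follow up", without saying whether each call asks about the whole period or only the time since the last call.

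The plan also gives an early expectation, in a sentence split by Table 2: "Additionally, it is expected that 5% in the" and then "Usual Care condition will make a quit attempt (24-hour quit) versus 15% in the Report condition at the time of the 3-week follow-up".

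Nothing in the plan removes events before the 3-week call from the mediation outcomes or adjusts for them.

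**The concern.** A mediation claim needs the mediator to come before the outcome it explains. If someone tries to quit in week 2 and reports readiness in week 3, the data cannot show which moved first. The attempt, whether it lasted or failed, may have changed the reported readiness. The fitted path from readiness to attempt would then contain some of the path from attempt to readiness.

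The same applies to resource use. Section IV places the counseling call within two weeks of the screen and has the specialist help with enrollment and medication during that call. In the counseling arms, resource use is therefore meant to start before readiness is measured.

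What is at stake is interpretation. The plan's hypothesis is that the Report raises readiness and motivation, which then lead to action, and this model is where that mechanism is examined.

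**Working it through.** **Inputs (all from Section VI)**
- Attempts by week 3: 5% Usual Care, 15% Report.
- Attempts by 6 months (Table 2), in the order Usual Care, Report, Counseling, Report + Counseling: 20/40/40/60% in scenario 1 and 20/35/35/50% in scenario 2.
- Averaged over counseling, scenario 1: (20+40)/2 = 30% against (40+60)/2 = 50%.
- Averaged over counseling, scenario 2: (20+35)/2 = 27.5% against (35+50)/2 = 42.5%.
- Total N = 400, so 200 per Report level; two-sided 0.05 for the main effect.

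**The plan's own figures first.** For two proportions with pooled variance under the null, power = Φ{[d√n − 1.96√(2p̄(1−p̄))] / √(p₁(1−p₁)+p₂(1−p₂))}, where d is the difference and p̄ the mean of the two proportions. With n = 200, 30% against 50% gives 98.5% (Table 2: 98.7%), and 27.5% against 42.5% gives 88.5% (Table 2: 89.2%). Table 2 reproduces. The plan states no power for the mediation model.

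**Share of 6-month attempters already counted by week 3** = week-3 rate / 6-month rate. **Share of the Report effect already present** = (15 − 5) / 6-month difference.

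| What 5% and 15% describe | Scenario | Usual Care | Report | Both | Effect present |
|---|---|---|---|---|---|
| No-counseling arms | 1 | 5/20 = 25% | 15/40 = 37.5% | 20/60 = 33% | 10/20 = 50% |
| No-counseling arms | 2 | 5/20 = 25% | 15/35 = 43% | 20/55 = 36% | 10/15 = 67% |
| Pooled over counseling | 1 | 5/30 = 17% | 15/50 = 30% | 20/80 = 25% | 10/20 = 50% |
| Pooled over counseling | 2 | 5/27.5 = 18% | 15/42.5 = 35% | 20/70 = 29% | 10/15 = 67% |

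The plan does not say which reading of 5% and 15% is meant, so both are shown. It gives no 3-month attempt rate. If that outcome is also cumulative, its early share cannot be below the 6-month share, because fewer attempters have accrued by then. No 3-week rate is given for resource use, so that part cannot be sized.

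**What remains after week 3**, counting first attempts only and taking the pooled reading:
- Scenario 1: 30 − 5 = 25% against 50 − 15 = 35%, a difference of 10 points. The formula above gives about 59% power for this total effect.
- Scenario 2: 27.5 − 5 = 22.5% against 42.5 − 15 = 27.5%, a difference of 5 points and about 21% power.

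Across all four rows, the share of attempters remaining within a condition runs from 1 − 0.43 = 57% to 1 − 0.17 = 83%.

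**The case against.** **The cumulative window is carried over.** The mediation sentence does not use it; it comes from the Sample Size paragraph. The sentence also omits the 3-week outcomes, which suggests that some time ordering was intended. The survey and the codebook are still to be written, and a since-last-call question there would remove the problem for attempts. This stands as a limit: the plan leaves the window open and does not expressly adopt the faulty one. But the cumulative window is the only one it states.

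**A reader might infer that early attempts precede their supposed cause, so the model cannot test the theory.** The documents do not support that. Early attempts precede the measurement of readiness, not necessarily its change: the Report could raise readiness in week 1, prompt an attempt in week 2 and be recorded in week 3. The order is unknown, not shown to be reversed, and most attempters fall after the call.

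**A reader might extend the point to abstinence.** Abstinence at 3 and 6 months is a current status (7-day point prevalence in the plan's 6-month expectation), so the cumulative-window argument does not reach it.

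**A reader might infer that people who have quit by week 3 drop out of the model.** The plan defines the primary readiness outcome as "subject-reported readiness to quit based on the contemplation ladder among those who have not quit smoking", but does not say that the mediator is limited in this way, and Section V has readiness assessed in calls to all participants. If the limit did apply, the model would select on a post-randomization outcome, and the shares above would no longer describe the sample analyzed.

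**The remedy is incomplete.** A week-3 attempt and week-3 readiness come from the same call, so their mutual order stays unresolved. That is true. Adjustment keeps the early attempt from confounding the path to later events; it does not recover what happened within the first three weeks.

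**The analysis is supplementary.** It is unpowered, and no primary or secondary comparison depends on it. That limits the importance of the point, but a larger sample or cautious wording would not resolve the ambiguity.

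**Conclusion.** The point holds as a low-cost improvement to a supplementary analysis. As written, the indirect effect for quit attempts and resource use has no established time order for a material share of events. That share is about 25-36% of 6-month attempters with both conditions together, and half to two thirds of the expected Report effect on attempts is already present by week 3.

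These figures assume that the cumulative window in the Sample Size paragraph also governs the mediation outcomes, and that the plan's expected rates are right. The shares depend on whether the 5% and 15% are single-arm or pooled rates; the points of effect already present do not. Abstinence at 3 and 6 months and the main-effect tests of the Report are not affected.

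**What to change.** For the mediation model only:
- Define quit attempts and resource use as events arising after the 3-week call.
- Have the 3-month and 6-month calls ask about events since the previous call. The plan does not say that attempt dates are collected, so the question wording has to carry this.
- Adjust for any attempt or resource use reported at the 3-week call.
- State whether the mediator is limited to people who have not quit. If it is, say that the result applies only to that post-randomization subgroup.

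Keep the cumulative outcomes for the main-effect tests; they can be rebuilt by combining the calls.

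The cost is a sentence or two in Section VI and a small change in survey wording. The model will have fewer events: about 57-83% of attempters remain if only first attempts count, and more if later attempts by early attempters are included. Precision falls in an analysis that was not powered to begin with.

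### Section VI claims adequate power for the Report within each counseling level, but Table 2 prints 67.6% for services with counseling, and its within-level powers ignore the interaction condition on those tests

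*Combined protocol and SAP*

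**What the plan says.** All of this is in Section VI of the combined protocol and SAP.

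- **Design differences (Sample Size).** "A difference of 20% and 12.5% is considered between the Report and Usual Care conditions to be of interest" for quit attempts and for accessing programs or medication respectively; 1.5 points is called meaningful on the contemplation ladder.
- **Power claims (Sample Size).** For the main effect, Table 2 is said to show sufficient power at these differences and "even reasonable power across many scenarios to detect smaller effects for the main effect of the Report". For the within-level effects, the text says that "there is adequate power to detect a significant effect of the Report within each level of the counseling condition at the 0.1 significance level".
- **Table 2 and its note.** "Power calculations assume total N=400 and the use of a two-sided test", with "0.10 significance level for the effects within each counseling condition level". In the 12.5-point services row (5%, 17.5%, 17.5%, 30%) the table prints 92.4% for the main effect, 88.9% without counseling and 67.6% with counseling.
- **When the within-level tests are run (Data Analysis).** Logistic and linear models first test the Report-by-Counseling interaction. Then: "If the interaction is significant, there will be an examination of whether there is a significant difference between the Report and Usual Care" at each counseling level. No significance level is given for the interaction test.
- **Expectation (Sample Size).** "it is expected that Report Only compared to Usual Care will significantly increase readiness to quit, quit attempts, and accessing of programs/medications". This is a contrast within the no-counseling level, and it is stated without reference to the interaction.

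**The concern.** The summary sentence covers both counseling levels and, by its silence, all three outcomes in Table 2. A reader who relies on it would take the Report's added effect among counseled participants as adequately powered for services and medication. The table gives that comparison roughly a one-in-three chance of missing the 12.5-point difference, even at the relaxed 0.10 level.

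The second problem concerns every within-level cell. Table 2 shows the power of a two-arm test that is always performed. The analysis text describes a test performed only after a significant interaction. These are different procedures with different power. If the condition is applied as written, the expected Report Only versus Usual Care result would usually not be tested under the plan's own scenarios.

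**Working it through.** **Inputs.** Rates, means, the ladder SD of 2.9, total N = 400 and two-sided alpha 0.10 within levels come from Table 2 and its note. The Wald test of a difference in proportions and the t-test come from Data Analysis. The allocation ratio is not stated; equal allocation (100 per arm) is assumed, and the printed powers reproduce under it.

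**Step 1: reproduce the plan's figure.** Services within Counseling, 17.5% vs 30%:

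- SE = √(0.175×0.825/100 + 0.30×0.70/100) = √0.00354375 = 0.0595
- 0.125 / 0.0595 = 2.100
- Power = Φ(2.100 − 1.645) + Φ(−2.100 − 1.645) = 0.6754 + 0.0001 = 67.6%

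Table 2 prints 67.6%. The pooled-variance formula gives 66.9%. The cell is correct.

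**Step 2: all six within-level cells at the design differences** (two-sided 0.10; unpooled Wald, or t-test for the ladder).

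| Outcome | No counseling: printed / recomputed | Counseling: printed / recomputed |
|---|---|---|
| Quit attempts, 20 points | 93.5 / 93.5% | 89.3 / 89.3% |
| Services/medication, 12.5 points | 88.9 / 88.7% | **67.6 / 67.6%** |
| Readiness, 1.5 points | 97.8 / 97.7% | 97.8 / 97.7% |

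Five cells support the sentence and one does not. For scale, 80% power in that cell at 0.10 needs 141 per arm (unpooled) or 143 (pooled), against 100. With 100 per arm, the difference detectable with 80% power is 15.0 points, not 12.5.

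**Step 3: is there an interaction in Table 2's scenarios?** On the difference scale there is none: the Report adds the same amount at both counseling levels in every row. For binary outcomes, however, the plan tests the interaction in a logistic model, which works on odds ratios.

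- Services, 12.5-point row: Report odds ratio (0.175/0.825)/(0.05/0.95) = 4.03 without counseling and (0.30/0.70)/(0.175/0.825) = 2.02 with it; ratio 0.50.
- Quit attempts, 20-point row: 2.67 and 2.25; ratio 0.84.
- Readiness: (9.0 − 7.5) − (7.5 − 6.0) = 0, so a linear interaction test is significant only at its alpha rate.

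**Step 4: how often the condition would be met.** One million simulated trials per row, 100 per arm, Wald test of the logistic interaction. The interaction alpha is an assumption, because the plan gives none. Ranges reflect adding 0.5 to the counts always, or only when a zero cell occurs.

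| Table 2 row | Assumed alpha 0.05 | Assumed alpha 0.10 |
|---|---|---|
| Quit attempts, 20 points | 6.5–6.7% | 12.3–12.6% |
| Quit attempts, 15 points | 6.1–6.3% | 11.7–12.0% |
| Services, 12.5 points | 14.9–16.6% | 25.8–28.2% |
| Services, 10 points | 10.4–11.7% | 19.4–21.5% |
| Readiness, both rows | 5% | 10% |

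The large-sample formula gives 19.5% for the 12.5-point services row at 0.05 (log odds-ratio difference −0.691, SE 0.630). Simulation is preferable with a 5% cell.

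**Step 5: power of the procedure as written.** In the 12.5-point services row, a significant interaction (assumed 0.05) followed by a significant within-Counseling effect at 0.10 occurs in about 5% of trials, against the printed 67.6%. This is below the simple product (0.166 × 0.676 = 11.2%), because trials with a significant interaction tend to be those where the counseled effect came out small.

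**The case against.** **The word adequate is undefined, and the weak cell is openly printed.** Both are true. The shortfall rests on the conventional 80% benchmark, so this is an overbroad summary sentence and not a concealed or miscalculated figure. Still, one description is applied both to cells of 88.9% or more and to one of 67.6%.

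**The 12.5 points belong to the main effect.** The text gives this difference between the Report and Usual Care conditions, and no sentence sets it as a target among counseled participants. That is fair, but Table 2's first services row applies 12.5 points at both levels, and the sentence on within-level power cites that table.

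**The stakes are limited.** The trial is sized for the pooled Report effect, where this row has 92.4%. Data Analysis lists use of services as secondary, although Sample Size counts accessing programs or medication among the outcomes the trial is powered for. This bears on severity and does not rescue the sentence.

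**A condition that is rarely met without interaction is working as intended.** This stands as a defense of the strategy. It does not make Table 2's unconditional figures the power of that strategy.

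**Stronger readings to avoid.** A reader might count the smaller-effect within-level cells (55.1–78.6%) against the sentence; the text claims power for smaller effects only for the main effect. A reader might also call it unclear whether the within-level tests are conditional. Data Analysis states the condition, and the expectation about Report Only versus Usual Care is a prediction and not a testing rule. The defect is that the power statements ignore the condition and that its alpha is missing.

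**Conclusion.** The point holds in two parts. First, the unqualified statement about each counseling level is not borne out for services within Counseling, where Table 2's own power is 67.6% at two-sided 0.10. This rests on equal allocation and, for calling it inadequate, on the 80% convention. Second, the within-level powers are unconditional while the stated tests are conditional. Under Table 2's scenarios the condition would be met in about 6–17% of trials across the binary rows at an assumed interaction alpha of 0.05, in 12–28% at 0.10, and at the alpha rate for readiness. The exact rates depend on that assumed alpha and on the handling of sparse cells; the mismatch does not.

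A reader might infer that Table 2 is miscalculated or that the trial is underpowered for its main question. The documents support neither: the table reproduces, and main-effect power is unaffected.

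**What to change.** In Section VI, Sample Size, limit the within-level power sentence to what Table 2 supports at the design differences: quit attempts and readiness at both counseling levels, and services without counseling. Name services within Counseling (67.6%) as the exception, and note that the within-level cells for smaller effects run from 55.1% to 78.6%.

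Then reconcile this with Data Analysis in one of two ways:

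1. Report both within-level Report effects as secondary estimates with confidence intervals at a stated level, whatever the interaction p-value. Table 2's unconditional power then applies to tests at its 0.10 level.
2. Keep the condition, state the alpha of the interaction test, and say that Table 2 does not give the power of the conditional tests. The expectation for Report Only versus Usual Care should then carry the same condition.

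The cost is protocol wording, a less favorable power statement and, under the first option, a little extra analysis. Sample size and main-effect power do not change.
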